## Phase II

### Recruitment and Consenting

- Recruitment for Phase II will largely proceed as with Phase I (pending unforeseen changes in the PT department's process). The only major change is that when researchers screen the schedule for evaluation appointments, they will also verify that the corresponding therapist completed the PiPT training.
- Research staff will brief the patient on the study.
- If the patient is interested, the researcher will show them to the private study room, screen them for eligibility, and then ask them to review the consent form. The researcher will remain in the room to answer any questions.

### Treatment

- After signing the consent form, the participant will complete a paper form collecting contact information for follow-up and demographic information. At this point, the participant will be assigned a participant ID number. The researcher will verify the participant's diagnostic code and therapist using AHLTA afterward.
- Before the participant's next PT appointment, the participant will complete the baseline questionnaire battery, a 139 question survey battery. The participant may complete the battery immediately on paper, or at a later date online using a link to REDCap that will be sent via encrypted email. This battery must be completed before their next appointment.
- Participants will receive PT care as prescribed and scheduled by their therapist. Participation in the study will not directly alter their care plan.
  - During Phase II, we anticipate that therapists who completed PiPT training will incorporate the training into their standard care. We will not ask therapists to give differential treatment to patients who are enrolled in the study.
- Participants will complete follow up questionnaire battery after their 4th PT appointment, 6mo and 12mo post enrollment. The first follow-up questionnaire is a 77 question survey battery. The second and third follow-up points use a 68 question battery. All follow-up questionnaires will be completed remotely via REDCap.
- We will collect de-identified SOAP notes from randomly selected participants and review them for verbiage indicating that the therapist employed principles of PiPT. We will collect up to 30 SOAP notes, pertaining to various physical therapists and throughout various stages of treatment.

We chose to conduct this study in sequential cohorts rather than conducting the two cohorts (PiPT and non-PiPT) in parallel because there are no comparable sites with similar characteristics such as type of subjects, catchment area size and availability of the health care team in the Navy.

\*We chose the 4th visit as the first follow-up point for two reasons. First, we expect to see a difference between groups on study outcomes at that point. Secondly, since according to the former head of the NMCP department of physical therapy (PI) the average number of visits at the outpatient PT clinic is 6, the 4th visit will allow us to capture complete data.

### **10.2 Data Collection:**

Describe all the data variables, information to be collected, the source of the data, and how the data will be operationally measured.

#### Intake Form (Demographics)

C  
o  
II  
V  
A  
R  
T  
I  
O  
A  
n  
B  
L  
P  
L  
E  
i  
n  
t

I D F  
n Si e r  
Gt n me  
e a glo e n  
n k e g R /  
d e It r e a  
e F e a s  
r o m p p  
r hio  
m c n  
s s  
e  
F  
I D r  
n e e  
t Sim e  
a n o e  
A k glg R n  
g e r e /  
e It a s a  
F e p p  
o mhi o  
r c n  
m s s  
e

F  
MI D r  
a n e e  
a n Sim e  
rit n o e  
t a glg R n  
alk e r e /  
ste It a s a  
a F e p p  
t o mhi o  
u r c n  
s m s s  
e

I D  
I e  
n Sim Y  
t a n o e  
h k glg s n  
n i e r e /  
c i It a N a  
t F e p N  
y o mhi o  
r c  
m s

I D  
I e S  
n Simel  
t n o e  
Ra glg ctn  
a k e r fr /  
c e It a o a  
e F e p m  
o mhi Li  
r c st  
m s

L  
e  
n I D F  
g I e r  
t t Sim e  
h t n o e  
of a glg R n  
s k e r e /  
e It a s a  
r F e p p  
m n

vio his  
c r c e  
e m s  
F  
R I D r  
R n e e  
a t Sime  
t t n o e  
e k glg n  
/ e r s /  
R Ita a  
a F e p p  
a o e p o  
n mhi o  
k r c n  
k m s s  
e e  
D  
E D a  
v I Da  
e t  
aln Sime  
u t n o ( a a  
a a glg d n  
tik e r d /  
o e Ita Ma  
n F e p O  
Do mhi N  
a r m  
t m c y  
e s y  
)  
T I D L  
h n e L  
e t m a  
r A o s t  
a a H g n n  
a k L r a n  
pi e T a m a  
st F a p e  
N o A p e,  
a r h i F i  
m r h i r s  
m m c t  
e s  
I D I  
n e C  
D t m D  
ia A o -  
g a H g n  
n k L r 1 /  
o e T a o  
si F A p C  
s o A p o  
s r h i d  
m c e  
s

**Evaluation Date:** Because participants will be consented and fill out the intake form on the day of their PT evaluation, the research staff member will simply record the current date that the form is completed.

We will require a DSA to harvest those last two variables.

#### **Questionnaires/Outcomes**

The self-report questionnaire batteries are largely composed of the validated survey tools and single-item questions.

1. The Pain Disability Index (PDI) will measure pain interference.
2. Catastrophizing will be assessed by the Pain Catastrophizing Scale (PCS).
3. Fear avoidance beliefs will be assessed using the Fear Avoidance Beliefs Questionnaire (FABQ). (Excluding "I have a claim for compensation for my pain," no relevance).
4. Psychological distress will be measured using the Hospital Anxiety and Depression Scale (HADS).
5. Self-efficacy will be assessed using the Pain Self-Efficacy Questionnaire (PSEQ).
6. *Positive outcome expectations* will be assessed using a 5 point single item scale developed for the military population by Stephanie Booth-Kewley et al. (2009).

7. Satisfaction with process of care will be measured by the "process of care" subscale of The MedRisk Instrument for Measuring Patient Satisfaction (MRPS).
8. Outcome satisfaction (single item scale): 'If you had to spend the rest of your life with the symptoms you have right now, how would you feel about it? This is derived from the Core Outcome Measures Index (COMI) questionnaire.
9. Clinical Depression: The Center for Epidemiologic Studies Depression Scale (CES-D).
10. Anxiety Disorder: General Anxiety Disorder Screener (GAD-7).
11. Post-Traumatic Stress Disorder (PTSD) will be assessed using the PTSD Checklist – Military version (PCL-M).
12. Job satisfaction (single item scale): "Taking everything into consideration, how do you feel about your job as a whole?" taken from Dolbier et al. (2005).
13. Work stress (single item scale): "Taking everything into consideration, how stressful is your job as a whole?"
14. Organizational commitment (single item scale): Commitment will be assessed by the affective dimension of the Commitment Scale.
15. Job social support: Subject's relationships with co-workers and social environment at their job, drawn from the Deployment Risk and Resilience Inventory-2 (DRRI) unit support subscale.

Injury history: affected body part(terminology adopted from Barrel matrix.), time since onset, other MSD comorbidities, episode recurrence, previous MSD and pain intensity.

#### Baseline Questionnaire Battery

- 139 questions charted below and one open field question on any barriers to treatment the participant perceives.

C  
 o V  
 V I I a R C  
 A e rie i  
 A c a s t  
 R T b p a  
 I O l o a  
 A O t  
 A n e n i  
 B L T s o  
 L o y e n  
 E i p s n  
 n e  
 t  
 B  
 T a  
 T s C S  
 o T e h o el  
 b li n e  
 a r foctn  
 c e u fr/  
 c e n o a  
 o It u d m  
 U r e e Li  
 s v m r st  
 e e  
 y  
 B  
 a D  
 s e S  
 E e Simel  
 d li n o e  
 u n g l g c t n  
 c e e r fr/  
 a S I t a o a  
 t i ue p m  
 o r m h i L i  
 n v c st  
 e s  
 y  
 B  
 a  
 s

e  
P li  
ri n  
m e  
a S D  
r u e S  
y r Simel  
I v n o e  
nj eglg ct  
u y e r fr8  
r , Ita o 5  
y F e p m  
L o mhiLi  
o ll c st  
c o s  
a w  
ti \_  
o U  
n p  
1  
,2  
,3

>  
4  
w  
e  
e  
k

B s,  
Tia D 4  
ms e -  
e e Sim 1  
si li n o 2  
n nglg n  
c e e r w /  
e S Ita e  
o u e p e  
n r mhi  
s v c s,  
ete s <  
y 1  
2  
w  
e  
e  
k  
s

E  
piB  
s a D  
o s e  
d e Sim Y  
e li n o e  
R nglg s n  
e e e r / /  
c S Ita N a  
u u e p N  
rrr mhi o  
e v c  
n e s  
c y  
e  
B  
p a D  
r s T e Y  
e e m e  
e li w o

vin o g s n  
o e Itr / /  
u Se a Na  
s u m p o  
Mr hi  
S v c  
De s  
y  
B  
a  
s  
e  
li  
n  
e  
S  
u D  
P r e 0  
aiv Sim 0  
n en o 1  
in y glg 0 n  
t , e r S /  
e F Ita a  
n o e p c  
n o e p al  
sill mhi e  
tyo c  
w s  
-  
U  
p  
1  
,,  
2  
,,  
3  
B  
M a D  
S s e S  
D e Simel  
c lin o e  
o n glg ct 8  
- e e r fr 5  
m S Ita o  
o ue p m  
r r mhi Li  
bi v c st  
di e s  
ty y  
B  
a  
s  
e  
li I  
On n  
u e d  
tcS e  
o u p  
mr Sie 0  
e v n n -  
e e gld 5  
x y e e s 1  
p , it n c 7  
e F e t al  
cto m V e  
a ll a  
ti o ri  
o w a  
n - bl  
e

U  
p  
1  
B  
a  
s  
e  
li  
n  
e D  
S e  
u p  
r e  
Q v Sin 5  
u end p  
al ygle t n  
It , e n s /  
y F Itt c a  
of o e V al  
Li ll ma e  
fe o ri  
w a  
- bl  
U e  
p  
1  
,, 2  
,, 3  
B  
a  
s  
e  
li  
n 0  
p e D -  
S e 1  
ai u p 0  
n r e s  
I v n c  
n e d al  
t y P e e 6  
e y P e e 6  
rf , D n ; 0  
FI t 7  
e o V q  
r ll a u  
e o rie  
n w a st  
c - blio  
e U e n  
p s  
1  
,, 2  
,, 3  
B  
a  
s  
e  
li  
n  
e 0  
S D -  
u e 6  
r p s  
S v e c  
el n  
f d

efe P e al6  
fi y S n e7  
c , E t ;  
a F Q V 1  
c o a 0  
y ll ri q  
o a u  
w ble  
- e st  
U io  
p n  
1 s  
,

2

,

3

B

a

s

e

li

n 0

P e D -

ai S e 4

n u p s

Cr e c

a v n al

t e d e

a y P e ;6

st, C n 11

r F S t 31

o o V q

p ll a u

hio rie

zi w a st

n - blio

g U e n

p s

1

,

2

,

3

B

a

s

e

li

n 0

e D -

F S e 6

e u p s

a r e c

r v n al

ofe d e

my F e ;6

o , A n 12

v B t 52

e o Q V q

mll a u

e o rie

n w a st

t - blio

U e n

p s

1

,

2

,

3

B  
a  
s  
e  
li  
n 4  
e Dp  
S et  
u ps  
r ec  
D v nal  
is e de  
tr y A n 6  
e ' D t 4  
s S Vq  
s o ll a u  
o rie  
w a st  
- blio  
U en  
p s  
1

,

2

,

3

A

ff 5

e p

O Bct t  
r aiv Li  
g s e C k  
g e co e  
c li o n e  
o n mfo rt  
m e mu ; 8  
m S it n 4 0  
it u md q  
m r e e u  
e v n r e  
n v n r st  
t et io  
t y s n  
c n  
al s  
e

5

p

J B t  
o a Li  
b s C k  
s e o e  
o li n rt  
cin D fo; 8  
cin R u 1 4  
s S R n 2 4  
u u d q  
p r e u  
p v r e  
o e st  
rty io

n

s

1

-

5

B s  
a c  
s C  
e o

li P n al  
n Cfoe 7  
eL u ; 7  
S- n 1  
uMd 7  
r eq  
v ru  
e e  
y st  
io  
n  
s  
0  
-

B 3  
a s  
Ds Cc  
e e o al  
p li Cn e  
r nE fo; 7  
e eSu 2 4  
s S- n 0  
siuDd q  
o r e u  
n v r e  
e st  
y io  
n  
s  
0

B -  
a 3  
s C s  
e o al  
A li Gn e  
n nA fo; 7  
xieDu ; 7 6  
e S- n  
tyu 7 d q  
r e e  
v r st  
e io  
y n  
s

B  
a  
s  
e  
li  
n  
e  
M S  
e u  
n r C  
t v h o Y  
al e h n Y  
H r fo e n  
e e e s n  
al' e u / /  
t F n a  
t o d N  
h ll e o  
C o m r  
a w  
r -  
e u  
p  
1  
,

,  
3  
B  
J a  
o s C  
b e Sio 1  
s l i n n -  
a n g l f o 5 7  
t i e e u s 9  
s f S i t n c  
a u e d a l  
c t r m e e  
i o v r  
n e

y  
B  
a  
W s C  
o e Sio 1  
r l i n n -  
k n g l f o 5 n  
s t e e u s /  
r S i t n c a  
e u e d a l  
s r m e e  
s v r  
e  
y

F  
u l  
B I  
a D  
s u  
e t  
l i y  
n ;  
e Li  
S m  
u it  
Dr e  
u v Sio d  
t y e n n D  
S y g l f o t n  
t , e u y /  
a F i t n a  
t o e d ;  
u l l m e M  
s o r e  
w d  
- B  
u o  
p a  
1 r  
, ;  
2 O  
, t  
3 h  
e  
r

P  
e  
rc D  
e i B e F  
v a p r  
e s e e  
d e S i n e  
b l i n d R  
a n g l e R  
r r e e n e

ieSItt s 1  
rsue V p 1  
r ma o  
t v rin  
o e as  
c y ble  
a e  
r  
e

Follow-up Questionnaire Batteries

- Post 4th treatment session- 77 items long, including one open field question
- 6 and 12mo – 68 items (excludes MRPS scale and outcome expectation)

C  
o V  
II a R C  
A e rie i  
R c ass i  
T ti b p t  
I O l o a  
A O l o t  
B L en i  
P T s o  
L o y e n  
E i p s n  
n e  
t  
B  
a  
s  
e  
P li  
ri n  
me  
a S  
r u D  
y r e S  
I v Simel  
n e n o e  
j y glg ct 8  
u , e r fr 5  
r F Ita o  
y o e p m  
L ll mhiLi  
o o c st  
c w s  
a -  
ti U  
o p  
n 1  
,,  
2  
,,  
3  
B  
a  
s  
e  
li  
n  
e  
S  
u D  
P r e  
ai v Sim 0  
n v Sim -  
n e n o -  
in y glg 1  
t , e r 0 n  
e F a c a /  
n o p c

sill Ithial  
t o e c e  
y wms  
-  
U  
p  
1  
,  
2  
,  
3  
B  
a  
s  
e I  
Oli n  
u n d  
tce e  
o S p  
mu Sie 0  
e r n n -  
e v gld 5 1  
x e e e s 7  
p y it n c  
e , e t al  
ctFmV e  
a o a  
till ri  
oo a  
n w bl  
- e  
U  
p  
1  
B  
a  
s  
e  
li  
n  
e D  
S e  
u p  
r e  
Q v Sin 5  
u end p  
al ygle t n  
it , e n s /  
y FItt c a  
of o e V al  
Li ll ma e  
fe o ri  
w a  
- bl  
U e  
p  
1  
,  
2  
,  
3  
B  
a  
s  
e  
li  
n 0  
p e D -  
S e 1  
ai u p 0

n r e s  
I v n c  
n e d al  
t yP e e 6  
e , Dn ; 0  
rfFI t 7  
e o V q  
r ll a u  
e o rie  
n w a st  
c - blio  
e U e n  
p s  
1

,

2

,

3

B

a

s

e

li

n 0

e D -

S e 6

u p s

S r e c  
elv n al  
f-e p d e  
efy S e ; 6  
fi , E n 1 7  
c F t 0  
a o V q  
c ll a u  
y o rie  
w a st  
- blio  
U e n  
p s

1

,

2

,

3

B

a

s

e

li

n 0

P e D -  
aiS e 4  
n u p s  
Cr e c  
a v n al  
t e d e  
a yP e ; 6  
st, C n 1 1

r F S t 3 1

o o V q

p ll a u

hio rie

ziw a st

n - blio

g U e n  
p s

1

,

2

,  
3  
B  
a  
s  
e  
li  
n 0  
e D-  
F S e 6  
e u p s  
a r e c  
r v n al  
ofe F d e  
my A e ; 6  
o , B n 1 2  
v F t 5 2  
e o Q V q  
mll a u  
e o rie  
n w a st  
t - blio  
U e n  
p s  
1

,  
2

,  
3

B  
a  
s  
e

li  
n 4  
e D p

S e t  
u p s

r e c  
v n al

D e H d e  
is y A e ; 6

tr y D n 1 4  
e , F t 4

s S o V q

s II a u  
o rie

w a st  
- blio

U e n  
p s

1

,  
2

,  
3

B  
a  
s  
e

li  
n  
M e  
S e  
e u  
n r C  
t v T o  
al h o Y

e e n Y  
H r fo  
e e u s

,  
,

alFe n / n  
t o Itd N/  
h ll e e o a  
Comr  
a w  
r -  
e u  
p  
1  
,2  
,3

S  
a D 1  
ti -  
sf e 5  
a P Li  
ct F e k  
ct o Mn  
io II E d e  
n o D e rt  
w wR n ; 7  
it - I t 8 1  
h u S V q  
p p K a u  
r 1 ri e  
o a st  
c b lo  
e e n  
s s

S  
a D  
ti F e  
sfo C p  
a II O e  
ct o Mn 5  
iowI d p  
n - Sie t 7  
wun n s 3  
it p glt c  
h 1 e V al  
O, it a e  
u 2 e ri  
tc, ma  
o 3 bl  
m e  
e

F  
ul  
B I  
a D  
s u  
e t  
li y  
n ;  
e Li  
S m  
u it  
D r e  
u v C d  
t Sio D  
y enn  
y y glfo u n  
S , e u t /  
t F it n y a  
a o e d ; a  
t ll me M  
u o r e  
s w d  
w B

- o  
u a  
p r  
1 d  
,

2 O  
,

3 t  
,

h e  
r

L

e

s

s o D

n F e F

s o p r

l e l l e e

a o S i n e

r w n d R

n - g l e e 1

e u e n s 1

d p I t t p

f r 1 e V o

o , m a n

m 2 r i s

t , a s

h 3 b l e

e e

r

a

p

y

#### SOAP Note Review

Researchers will review the randomly selected, de-identified SOAP notes for verbiage indicating that the therapists identified and applied principles of PiPT, such as references to yellow flags like fear avoidance behavior. These SOAP notes and their reviews will not be assigned a Subject ID number or otherwise be associated with their corresponding demographic information or questionnaire responses.

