Our research group has experience in training Navy personnel to address psychological risk factors. We designed an education and training program for an interdisciplinary team at the Navy Medical Center Portsmouth (NMCP). Team members were trained in the biopsychosocial model as a group and then individually by experts in their field. The purpose of this training was to teach physical therapists, psychologists, and physicians how to work in an interdisciplinary team. In a pilot randomized controlled trial, we tested the feasibility of implementing an interdisciplinary work restoration program based on this training called "Backs to Work" in a Navy and Marine Corps setting for ADSM with work-limiting low back pain. We found preliminary evidence that those randomized to CBT and PT had improved perception of function as compared to usual care and there was a trend of decreased fear of activity and pain catastrophizing in the intervention group as compared to usual care.

Furthermore, we developed a PiPT course to train PT personnel aboard an aircraft carrier in a case-controlled cohort pilot study comparing PiPT to usual care. Results demonstrated the feasibility of implementing this intervention onboard US Navy aircraft carriers. Trained PT personnel achieved a priori criteria for feasibility by obtaining passing knowledge scores following training, completing clinical notes indicating PiPT implementation and participating in regular case reviews in which they discussed their treatment plans via phone conference with the research team. Feedback from the PT staff who stated that their treatment paradigm and practice had changed from a biomedical to a biopsychosocial model after training also confirms successful transfer of PiPT training into clinical practice.

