#### Specific aims

1. Demonstrate the feasibility of implementing PiPT in a US Navy shore-based health care setting. We will analyze SOAP notes to assess whether the clinicians have applied aspects of the training in the treatment given to the patients and they are reflected in the notes.
2. Document and compare baseline risk factors related to pain interference in two cohorts of patients with MSD.
3. Demonstrate the effectiveness of a PiPT intervention on psychological and functional work outcomes in a comparative effectiveness trial through a relative increase in protective follow-up measures such as quality of life, self-efficacy, and satisfaction and a relative decrease in detrimental measures like pain catastrophizing, fear of movement, and distress.

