###### Treatment

- After signing the consent form, the participant will complete a paper form collecting contact information for follow-up and demographic information. At this point, the participant will be assigned a participant ID number. The researcher will verify the participant's diagnostic code and therapist using AHLTA afterward.
- Before the participant's next PT appointment, the participant will complete the baseline questionnaire battery, a 139 question survey battery. The participant may complete the battery immediately on paper, or at a later date online using a link to REDCap that will be sent via encrypted email. This battery must be completed before their next appointment.
- Participants will receive standard PT care as prescribed and scheduled by their therapist. Participation in the study will not alter their care plan.
- Participants will complete follow up questionnaire batteries after their 4th PT appointment\*, 6mo and 12mo post enrollment. The first follow-up questionnaire is a 77 question survey battery. The second and third follow-up points use a 68 question battery. All follow-up questionnaires will be completed remotely via REDCap.
- We will collect de-identified SOAP notes from randomly selected participants and review them for verbiage indicating that the therapist employed principles of PiPT. We will collect up to 30 SOAP notes, pertaining to various physical therapists and throughout various stages of treatment.

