##### PT Training

Following the completion of Phase I recruitment, PT staff will be trained in PiPT by the NYU personnel. NYU personnel intend to deliver the training in person; however, they are prepared to deliver virtual, real-time training should COVID protocols make face-to-face training unfeasible.

- PT staff will receive a knowledge quiz at the end of their training sessions to document successful completion of training. PT staff must obtain a passing score (85% or above) on this quiz to be considered proficient.
- We will also assess the PT staff's confidence in implementing PiPT using a seven point Likert scale self-rating derived from a previous study.
- Furthermore, staff will be evaluated on the accurate identification and management of yellow flags using case studies.
- Once the staff shows proficiency in delivering PiPT, the second study phase will begin. There will likely be some overlap between the follow-up data collection of Phase I and the training period.
- After initial training and as Phase II recruitment begins, staff will receive weekly reinforcement sessions for one month, after which they will receive further reinforcement sessions on a biweekly basis as needed.

During training, PT staff will be asked whether they have had previous experience with PiPT. If so, participants who saw these providers, whether during Phase 1 or 2, will be analyzed for a possible confounding effect.

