#### **10.14 Managing Data (Data Management and/or Sharing Plan) and/or Human Biological Specimens for this Study:**

Include in this section the plan for acquiring data (both electronic and hard copy), access during the study, data/specimen storage and length of time stored, shipment/transmission, and the plan for storage and final disposition at the conclusion of the study. Describe any data agreements in place for accessing data within and/or outside of your institution (e.g., Data Sharing Agreement, Data Use Agreement, Business Agreements, etc.)

**Acquiring Data:** The majority of participant data will be accrued via self-report questionnaire. We plan to retrieve diagnostic codes from their PT SOAP notes on AHLTA, and we will extract and de-identify whole SOAP notes from a subgroup of randomly selected participants. We will also use CHCS and AHLTA to determine when a participant has or will receive their fourth PT session, but this is merely for scheduling follow-up, and will not be retained as data.

**Data Entry and Integrity:** For data entered by participants into the REDCap surveys, we presume that participants responded correctly. All data collection tools completed on paper will be scanned and initially entered into REDCap by the proctoring research team member, who will mark the instrument as "Unverified" in REDCap. The scanned forms will be transmitted to [name] via SAFE, who will use them to verify the entered data, correct any inconsistencies, and then mark the instrument as "Complete." Our Excel database has been designed to draw values directly from downloaded REDCap data reports, reducing the potential for human error. We have also employed Excel's conditional logic programming and formatting to alert us if a participant's records are incomplete or mismatched.

**Access to Data:** The PI and research contractors ([name] and [name]) will have access to all study data, electronic and hard copy. NYU collaborators ([name] and [name]) will not have access to the original data; de-identified data and de-identified SOAP notes (for training evaluation) will be securely transmitted to them using the SAFE computer app.

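### The SOAP note review that carries Aim 1 has no masking to phase and no fixed scoring form, and the notes go to the group that delivers the training

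*Combined protocol and SAP*

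**What the plan says.** Section 9.3, Aim 1, names the note review as the means of showing feasibility: "We will analyze SOAP notes to assess whether the clinicians have applied aspects of the training in the treatment given to the patients". No other measure is listed under that aim. Section 9.4 calls the study a hybrid type 3, a design that tests the implementation strategy while gathering information on clinical outcomes.

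Section 10.1 states, under Phase I and again in the same words under Phase II: "We will collect up to 30 SOAP notes, pertaining to various physical therapists and throughout various stages of treatment". Whether the ceiling of 30 applies to each phase or to both together is not explicit.

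On who is involved, the PT Training part of section 10.1 says "PT staff will be trained in PiPT by the NYU personnel". Section 10.14 (Access to Data) says of the NYU collaborators that "de-identified data and de-identified SOAP notes (for training evaluation) will be securely transmitted to them using the SAFE computer app".

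On method, section 10.2 (SOAP Note Review) gives the sentence "Researchers will review the randomly selected, de-identified SOAP notes for verbiage indicating that the therapists identified and applied principles of PiPT" and one illustration: "such as references to yellow flags like fear avoidance behavior". On de-identification it adds "These SOAP notes and their reviews will not be assigned a Subject ID number" and that notes will not be tied to demographic or questionnaire data. Sections 11.1 and 11.6 do not mention the note review.

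**The concern.** Deciding whether free text shows a PiPT principle is a judgement. A reader who knows that a note was written after training may credit an ambiguous phrase that would have been passed over in a note from before training. Three features make this possible here: the notes go to the group that delivers the training, nothing is said about hiding phase, and there is no fixed form to limit discretion.

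At stake is the feasibility conclusion. The background (section 9.2) reports an earlier randomized trial of such training in which therapists' attitudes and knowledge shifted but their behaviour did not. That trial says nothing about rater bias. It does show why evidence on behaviour in care matters, and the note review is the only evidence Aim 1 names for it. If its readers lean towards post-training notes, a null result on behaviour could be reported as uptake.

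**Working it through.** The plan gives no figure for the note review, so there is none to reproduce. The check has two parts.

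**1. What the text provides**

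| Safeguard | What the documents say |
|---|---|
| Readers identified | Only that they are researchers (10.2) |
| Readers independent of trainers | Not stated; notes go to NYU (10.14), NYU trains (10.1) |
| Phase hidden | Not stated; 10.2 removes the Subject ID and the link to demographics and questionnaires |
| Phase I and Phase II notes mixed | Not stated |
| Scoring form or threshold | One example, no form (10.2) |
| Analysis of the contrast | Absent from 11.1 and 11.6 |

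The steps in section 10.2 protect privacy. They do not address phase.

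**2. How much over-crediting could matter (illustration on assumed values)**

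Inputs from the documents: up to 30 notes in each phase (10.1, read as per phase), and two-sided significance at 0.05 (11.6). Assumed inputs: a true rate p of PiPT content that is the same in both phases, Phase I notes scored without error, and a share f of truly negative Phase II notes credited by mistake. Fisher's exact test is also supplied here; the plan does not specify it for the notes.

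Apparent Phase II rate: p2 = p + (1 − p) × f. The spurious rise is (1 − p) × f. For p = 0.30:

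- f = 0.10: 0.70 × 0.10 = 0.07, so p2 = 0.37
- f = 0.20: 0.70 × 0.20 = 0.14, so p2 = 0.44
- f = 0.30: 0.70 × 0.30 = 0.21, so p2 = 0.51

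These 7, 14 and 21 points bias a purely descriptive contrast, with no test involved.

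Chance of a falsely significant rise: the sum of Bin(i; n, p) × Bin(j; n, p2) over all pairs with j > i and a two-sided Fisher p-value below 0.05, by exact enumeration.

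| Notes per phase | True rate p | f = 0 | f = 10% | f = 20% | f = 30% |
|---|---|---|---|---|---|
| 30 | 10% | 0.5% | 7.8% | 30.5% | 61.2% |
| 30 | 20% | 1.1% | 6.3% | 19.8% | 41.3% |
| 30 | 30% | 1.3% | 4.8% | 13.3% | 28.5% |
| 15 | 10% | 0.3% | 3.4% | 12.1% | 26.7% |
| 15 | 20% | 0.8% | 3.0% | 7.6% | 15.7% |
| 15 | 30% | 0.8% | 2.2% | 5.2% | 10.6% |

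The rows with 15 notes apply if 30 is the total over both phases. Without over-crediting, the chance of a false rise is about 1% or less throughout, because Fisher's test is conservative at these sizes.

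**The case against.** The strongest reply is that the plan contains no phase comparison of the notes. Aim 1 asks whether the training was applied, section 10.2 describes a search, and the analysis plan is silent. Any rejection rate therefore belongs to a test brought in from outside. This stands as a limit on the numbers. It does not remove the problem: the same notes are collected in both phases, and a descriptive contrast carries the same reader bias.

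Second, larger error rates can be produced by assuming larger shifts. Raising the Phase II rate by 10, 20 or 30 percentage points from a base of 30% gives two-sided rejection rates of 7.8%, 25.9% and 56.1% at 30 notes per phase (2.6% with no shift). A reader might infer that slight leniency produces a false finding more often than not. It does not. A 20-point shift means wrongly crediting 20/70 = 29% of negative notes, and a 30-point shift 30/70 = 43%. At 15 notes per phase the three figures fall to 3.4%, 9.7% and 22.7%.

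Third, a reader might infer that NYU designed the course, alone scores the notes, and would know the phase from when they arrive. The documents do not establish any of these. Section 9.2 credits the research group with the earlier course ("we developed a PiPT course to train PT personnel aboard an aircraft carrier") and says that experience informed the present proposal; NYU is named only for delivery. Section 10.14 also gives the investigator and research contractors at NMCP access to all study data. No section says when notes are sent or whether they go in phase batches. De-identification may remove date cues if the Safe Harbor method described in section 10.8 is used, but the method for these notes is not stated.

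Fourth, other evidence on training exists: the knowledge quiz with its 85% pass mark, confidence ratings, case studies, and a follow-up question on lessons learned from therapy. This is fair context. The first three measure proficiency, the last is the patient's report, and none is named under Aim 1.

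Finally, masking will be imperfect, because the vocabulary being scored can itself point to Phase II. That stands, and it is the reason the checklist is needed as well as the shuffling.

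**Conclusion.** The concern holds as an unprotected judgement in the evidence for Aim 1. Notes from both phases go to the group that delivers the training, the scorer is unnamed, no masking to phase is described, and there is no fixed form. The implied before/after contrast is open to reader expectation.

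The size cannot be derived from the documents. On assumed values (30% true use in both phases, 30 notes each), over-crediting 10%, 20% or 30% of negative Phase II notes gives about a 5%, 13% or 29% chance of a falsely significant rise. The figures are higher at lower true rates and lower if 30 is the total. They rest on the assumed true rate, the assumed over-crediting, error-free Phase I scoring and a test that the plan does not specify. They show sensitivity, and are not evidence that biased scoring will occur. The change is worth making because it is cheap and because readers who have seen the notes unmasked cannot later be masked to them.

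**What to change.** Amend the SOAP Note Review part of section 10.2 to state that:

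1. NMCP staff remove dates, phase and therapist names from each selected note.
2. Each note receives a random note code. Phase and a coded therapist number are held in a separate key, so notes can later be compared within therapist. No Subject ID or questionnaire link is needed, so the existing privacy rule is kept.
3. Phase I and Phase II notes are shuffled together before they are released for scoring.
4. Readers, whose role is named, score each note yes/no on a checklist of PiPT elements fixed before any note is opened.
5. Phase is unmasked only after all scoring is complete.

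The same amendment should say whether 30 notes is per phase or in total.

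Cost: scoring of Phase I notes for Aim 1 waits until the Phase II notes are drawn, and preparation takes a few hours. No extra readers are required. Any NMCP review of notes for incidental findings under section 14.6 should not be delayed by this step.
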